## ***Introduction:***

A better understanding of knee joint kinematics is important to explain the premature polyethylene wear failures, patient dissatisfaction with function and to help design a prosthesis that most closely approximates the normal knee. Previously, most experimental studies of knee kinematics have involved cadaveric, in vitro analyses, or have not tested the knee in a weight-bearing mode. Others have used exoskeletal linkages and skin markers that permit error due to undesired motions between markers and the underlying bone. More recently, fluoroscopy has been used to assess in vivo kinematics for subjects having a TKA. These in vivo studies have defined the following abnormal kinematic patterns that exist with total knee arthroplasty (TKA), in comparison to the normal knee:

1. Most subjects having a posterior cruciate retaining PCR TKA and some having a posterior stabilized (PS) TKA experience a paradoxical translational of the femoral component relative to the tibial component
2. All TKA types experienced a significant percentage of subjects having reverse axial rotation, where the femoral component internally rotates with increasing knee flexion, opposite of the normal knee.
3. All TKA types demonstrate the occurrence of condylar lift-off, where one condyle raises off the tibial plateau.

New TKA continue to be designed and marketed to the patient and surgeon, but are these designs significantly different than those previously offered? What is the rational for those design changes and do they truly offer an advantage? More recently, Zimmer-Biomet brought a new knee implant to the orthopaedic market, called the Persona TKA. This family of TKA includes both a posterior stabilized and posterior cruciate retaining design for the surgeon to choose. More recently, surgeons have implanted both the PCR and PS Persona TKA into patients, but as of today Zimmer does not have in vivo data validating their design or have compared the kinematic results with those patients previously evaluated having either a NexGen PCR or PS TKA. Therefore, the objective for this study is to analyze the in vivo kinematics for patients implanted by two surgeons having either a Zimmer-Biomet Persona PCR or PS TKA.

## ***Hypothesis:***

1. It is hypothesized that subjects having a PS TKA will experience greater posterior femoral rollback, axial rotation and weight-bearing flexion than subjects having a PCR TKA.
2. It is hypothesized that subjects having a Persona TKA will experience better kinematic patterns than subjects previously analyzed having a NexGen TKA.

***Study design:*** In vivo knee kinematics will be assessed for 25 subjects that have been implanted with a Zimmer-Biomet Persona fixed bearing posterior stabilizing (PS) total knee arthroplasty (TKA) by [name] [name] of the Institute for Locomotion, Aix-Marseille University, Hopital Sainte-Marguerite. The other 25 subjects with the Zimmer-Biomet Persona fixed bearing poster cruciate retaining (PCR) TKA will be provided by another surgeon at a separate site, which has yet to be determined. [name] and [name] both of the Institute for Locomotion, Aix-Marseille University, Hopital Sainte-Marguerite will serve as Sub-Investigators. [name] of the University of Tennessee will also serve as a Sub-Investigator. Enrollment will be increased to 28 subjects per implant type to ensure that researchers acquire the necessary 25 usable datasets for analysis for each implant type and also

to account for any subjects that may drop out of the study. All TKAs should be judged clinically successful (KSS > 75). Each subject should have a well-functioning prosthesis, be at least six months post-operative, and should have good-to-excellent post-operative passive flexion.

Deciding which subjects received which kind of implant was up to the discretion of the study surgeon, according to his professional opinion. The determination as to which type of implant subjects received is outside the scope of this particular study. Subjects will already have the knee implants and must be at least six months post-operative.

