## **BENEFITS**

The potential benefits from this study include, but are not limited to:

- Better understanding of the joints analyzed with the same technique in the past.
- Future implant design improvements based on the kinematic findings.
- New and advanced surgical techniques for TKA based on the results.
- Information related to the data gathered may be provided to the surgeon by the researchers if something out of the ordinary is seen during the imaging. However, researchers are not radiologists and cannot interpret anything they may see. If there is something within the imaging that is obviously wrong as mentioned above, then this could result in potential modification of a subject's treatment plan if images collected as a result of this study reveal any kind of "significant problem."

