## DATA ANALYSIS

Once the subjects have completed the activity, the fluoroscopic videos will be stored digitally and specific frames of interest will be captured from the video and exported into the preprocessing software. The specific frames of interest will be full extension, maximum knee flexion (both inclusive), and 30° knee flexion increments during the complete flexion cycle.

Our 3D to 2D registration technique will be used to overlay the 3D models of the implanted components on their projection in the 2D fluoroscopic image. The fluoroscopic video would be digitized into frames and corrected for distortion. From here, the distortion-free images would be used with the 3D to 2D registration technique to extract in vivo patient femorotibial kinematics, which involves overlaying the 3D models of the components on their projection in the 2D fluoroscopic image.

Statistical analysis of the data will be carried out to analyze the two cohorts. All variables, except for lift-off and VAG, will be denoted as continuous. The data will be first checked for normality using the Shapiro-Wilk test. Only when the data is found to be normally distributed will parametric tests be used; otherwise, non-parametric tests will be used. The data will also be tested for equality of variance using the Barlett's test and Levene's test. The final selection criterion for the type of test to conduct will be based on the check for normality, as well as the check for equal variance. Therefore, for all the continuous variables, the following tests will be used:

1. Student's t-test (when the data is normally distributed and has equal variance).
2. Welch Anova test (when the data is normally distributed but has unequal variance).
3. Wilcoxon Mann Whitney U-test (when the data is not normally distributed).

Lift-off, as applicable, will be treated as a categorical variable in this study and a contingency analysis using the Fisher's exact test will be carried out. All statistical tests will be carried out at 95% confidence level ( $\alpha=0.05$ ) and will be performed using JMP® Statistical Discovery™ (SAS Institute Inc., Cary, NC) software.

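### Hypothesis 2 (Persona better than NexGen) cannot be answered by the analysis as planned: no NexGen dataset, endpoint for 'better' or test is specified

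*Protocol*

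**What the plan says.** The Protocol (Hypothesis) states two hypotheses. The first names its variables: "subjects having a PS TKA will experience greater posterior femoral rollback, axial rotation and weight-bearing flexion than subjects having a PCR TKA". The second is "It is hypothesized that subjects having a Persona TKA will experience better kinematic patterns than subjects previously analyzed having a NexGen TKA", with no variable, direction or threshold attached.

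The Protocol (Introduction) gives the missing comparison as part of the rationale: the manufacturer is said not to "have compared the kinematic results with those patients previously evaluated having either a NexGen PCR or PS TKA". The objective that follows covers Persona only, in its PCR and PS types, and does not mention NexGen.

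The study design paragraph provides for 25 Persona PS subjects from one surgeon, and "The other 25 subjects with the Zimmer-Biomet Persona fixed bearing poster cruciate retaining (PCR) TKA will be provided by another surgeon" at a second site. Enrolment is raised to 28 per type. No NexGen group is enrolled.

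The SAP (Data Analysis) says "Statistical analysis of the data will be carried out to analyze the two cohorts" without naming the cohorts. It lists Student's t, Welch ANOVA and Mann-Whitney tests for continuous variables and Fisher's exact test for lift-off, all at alpha 0.05. Sidedness is not stated, there is no multiplicity rule, and neither NexGen nor historical data are mentioned.

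The nearest text elsewhere is a line in the Protocol's Benefits list: "Better understanding of the joints analyzed with the same technique in the past". It describes no comparison.

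**The concern.** One of the two stated hypotheses is a superiority claim against an outside group, and nothing in the plan produces a test of it. Followed exactly, the SAP gives results for Hypothesis 1 and none for Hypothesis 2.

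An unspecified comparison against earlier data leaves three matters to be settled after the Persona results are known.

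- **The comparator.** Which NexGen subjects are used, and whether their sampling error is carried into the comparison.
- **The meaning of 'better'.** With no named variable, a favourable one could be chosen afterwards.
- **The handling of implant type.** NexGen, like Persona, has PS and PCR types. The Introduction says that paradoxical translation occurs in most PCR subjects but only some PS subjects. Pooling the families with different type mixes would confuse family with type.

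At stake is whether a statement that Persona improves on NexGen would have any controlled error rate behind it.

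**Working it through.** **What the documents allow.** The only sample-size figure is 25 usable datasets per implant type from 28 enrolled. The step from 25 to 28 can be reproduced: 1 - 25/28 = 10.7%, in line with about 10% loss. The 25 itself cannot, because no effect size, SD or power is given. No figure bears on Hypothesis 2, so the main point rests on the text and the arithmetic below is illustration.

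**Textual check.** The design enrols two groups, Persona PS and Persona PCR, and the SAP analyses two cohorts. If these are the two Persona groups, Hypothesis 1 is tested and Hypothesis 2 is not. If they were instead Persona and NexGen, Hypothesis 1 would lose its test. One two-cohort comparison cannot serve both.

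**Illustration 1: a NexGen mean used as a fixed benchmark.** Inputs: n = 25 Persona subjects (Protocol). Assumed: m NexGen subjects, equal SD, independent subjects, normal approximation, two-sided alpha 0.05. If the m-subject mean is treated as a constant, the test statistic has null variance 1 + n/m instead of 1, so

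true type I error = 2 × [1 - Φ(1.96 / √(1 + 25/m))].

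For a proper two-sample comparison, the difference detectable with 80% power is (1.96 + 0.84) × √(1/25 + 1/m) in SD units.

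| m (assumed) | √(1 + 25/m) | 1.96 divided by it | Type I error | Detectable difference, two-sample |
|---|---|---|---|---|
| 10 | 1.871 | 1.048 | 29.5% | 1.05 SD |
| 20 | 1.500 | 1.307 | 19.1% | 0.84 SD |
| 25 | 1.414 | 1.386 | 16.6% | 0.79 SD |
| 50 | 1.225 | 1.600 | 11.0% | 0.69 SD |

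Counting only errors in Persona's favour halves the fourth column, to about 15%, 10%, 8% and 5.5%, against a nominal 2.5%.

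**Illustration 2: choosing a favourable result.** Three variables (rollback, axial rotation, weight-bearing flexion) by two implant types make six tests. If they are independent and there is no true difference:

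- two-sided 0.05, favourable direction only: 1 - 0.975^6 = 14%;
- one-sided 0.05: 1 - 0.95^6 = 26%.

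Rollback and rotation come from the same registered frames, so independence is doubtful. Positive correlation would lower both figures.

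**Illustration 3: pooling types.** Let D be the PS-minus-PCR difference, taken as equal in both families. Persona has a PS share of 25/50 = 0.5; NexGen has an unknown share p. With no family effect at all, the pooled Persona-minus-NexGen difference is (0.5 - p) × D. This runs from +0.5D at p = 0 to -0.5D at p = 1, and is zero only at p = 0.5.

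**The case against.** The fair case on the other side has four parts.

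- **The question may be answerable.** Hypothesis 2 speaks of subjects already analysed, the Benefits list refers to earlier work with the same technique, and the Protocol's data-storage text describes adding to a retained research collection. Subject-level NexGen data may therefore exist. This stands: a reader might infer that the hypothesis can never be tested, but the documents show only that the planned analysis does not test it. They do not confirm that such data exist or are accessible.
- **No informal or fixed-benchmark comparison is described.** A reader might infer that Persona results will simply be set beside NexGen averages, and that the 30% to 11% errors belong to this plan. The documents are silent on the method, and no benchmark test is listed. Those figures describe a possible misuse, with assumed NexGen numbers. The 26% likewise needs one-sided tests, and the SAP does not state sidedness.
- **The cohorts are inferred.** The SAP names no implant. That the cohorts are Persona PS and Persona PCR follows from the Protocol's design. This stands as a qualification but does not rescue Hypothesis 2.
- **NexGen is not in the objective.** It would overstate matters to say that half the study's purpose is lost, since the objective sentence covers Persona alone. But Hypothesis 2 is listed on equal terms with Hypothesis 1, and the Introduction uses the missing comparison as motivation.

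None of this supplies a dataset, an endpoint or a test.

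**Conclusion.** The point holds in this form: Hypothesis 2 cannot be answered by the analysis as planned, because the documents give no NexGen data source, no definition of 'better' and no test. This is more than missing detail, since following the plan exactly leaves one of its two hypotheses without a valid result. Hypothesis 1 is unaffected.

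The conclusion rests on the text and on the inference that the two cohorts are the two Persona groups. It does not depend on the illustrative error rates, which hold only under the assumed NexGen sizes, equal SDs, independence and a comparison method that the plan does not describe. The change should be made before any NexGen comparison is run.

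**What to change.** **Default.** Relabel Hypothesis 2 as descriptive and state that no superiority conclusion will be drawn. This costs a sentence and is always available. In either case, name the two cohorts in the SAP.

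**If suitable subject-level NexGen data exist.** They should come from the same registration technique and activity, in subjects who meet the same criteria (KSS above 75, at least six months post-operative). Then add to the SAP:

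- the dataset, with its n, site and period, and how subjects were selected;
- two type-matched comparisons, Persona PS with NexGen PS and Persona PCR with NexGen PCR, on rollback, axial rotation and maximum weight-bearing flexion;
- the direction and the pattern of results that will count as 'better', and the sidedness of the tests;
- 95% confidence intervals, and multiplicity control across the six tests, for example Holm (the smallest p-value is compared with 0.05/6 = 0.0083);
- adjustment for age, BMI and time since surgery where held. The Protocol already collects the Persona side of these.

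**If only NexGen summaries exist.** Use an unadjusted summary-data Welch comparison, with standard error √(s_P²/n_P + s_N²/n_N), so that the NexGen SD and n are carried through. Covariate adjustment is not possible in that case.

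**Cost.** An SAP paragraph and a little more analysis; the variables named need no new imaging of Persona subjects. The comparison stays historical and non-randomised, with surgeon, site and era confounded with implant, and must be reported as such.

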#### ***Inclusion and exclusion criteria:***

We will use the following inclusion criteria to recruit participants for this study:

1. Subjects will have a Zimmer Persona fixed bearing PS TKA.
2. Subjects must be at least six months post-operative.
3. Subjects will have KSS greater than 75.
4. Participants must be able to perform the required activities - stepping up and a deep knee bend.
5. Subjects must be willing to sign the Informed Consent (IC) / HIPAA form to participate in the study.
6. Bilateral subjects may be included in the subject population.

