### **Data Collection**

On the day the fluoroscopic procedures will take place, researchers selected by [name], student research assistants ([name], [name], [name], [name]) with the Center for Musculoskeletal Research (CMR) will travel to the Institute for Locomotion to collect the data. A study Investigator will be present for the fluoroscopy procedures. Drs. [name] or [name] will consent the participants. They will meet with each potential participant individually to make sure s/he has been properly informed of the procedures and to help with any of the IC/HIPAA form. Subjects will be informed that they do not have to participate and are free to leave if they wish and will answer any questions subjects may have about the study. Participation is entirely voluntary.

After consent has been obtained and eligibility has been confirmed, a study physician will administer the New Knee Society Score survey to all participants.

In addition to fluoroscopy video, subjects will be videotaped from the shoulders down (to maintain subject anonymity) while performing the activities (live feed perspective). During the fluoroscopy procedure, the radiation technician (RT) will follow the motion of the implanted knee with the fluoroscopy machine; only the knee joint (from the fluoroscopy machine) will be

recorded on the fluoroscopy footage. The practice portion of the data collection without radiation will not be video-recorded. The participant will be allowed to rest as necessary and be instructed to stop the activity at the first sign of pain. The speed level of each trial will be based on the comfort level of the subject. One of the researchers will be ready and in close proximity to assist each subject in case the participant requires help. This precaution will be practiced for all participants, regardless of physical wellbeing, age or prior results; no assumptions will be made as to any participant's capabilities.

Multiple trials of each activity may be conducted to ensure usable images have been acquired to complete the study. Radiation time will be kept as low as reasonably achievable (ALARA) and will not exceed two minutes. The RT will start the fluoroscope just prior to the subject beginning each activity trial and will stop the fluoroscope immediately after the subject completes each activity trial to ensure that the subject is not exposed during idol periods. Fluoroscopy on-time will be recorded on each subject's IC.

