##### 6- Side of this (surgically treated) knee

Left  Right

If both knees have been operated on,  
please use a different form for each knee

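### Does admitting bilateral subjects without naming an index knee undermine the two-sample tests?

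*Protocol*

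**What the plan says.** The Protocol's inclusion list admits people with two replaced knees: "Bilateral subjects may be included in the subject population". The same list sets a score threshold for the person: "Subjects will have KSS greater than 75".

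The study design text under the Hypothesis heading counts people: "In vivo knee kinematics will be assessed for 25 subjects" in the PS group, and another 25 in the PCR group. Enrolment is raised to 28 per implant type to secure "the necessary 25 usable datasets for analysis for each implant type". The same text adds "All TKAs should be judged clinically successful (KSS > 75", and then asks that each subject have a well-functioning prosthesis, in the singular.

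Under Data Collection, a study physician "will administer the New Knee Society Score survey to all participants". The attached Knee Society form tells a patient with two operated knees: "please use a different form for each knee". The activity instructions refer to one knee under study but do not say how it is chosen when both are implanted.

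The SAP's Data Analysis section compares the two cohorts with Student's t-test, Welch's test or the Mann-Whitney test for continuous variables, and with Fisher's exact test for lift-off, all at 0.05. It does not mention bilateral subjects.

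**The concern.** A person with two implants can supply two kinematic records and two Knee Society scores. The two knees of one person tend to resemble each other, so two records carry less information than two people would. All four SAP tests treat every value as independent. If both knees went in as separate values, the standard error would be too small and the false-positive rate would exceed the nominal 5%.

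Two further points add to the worry. If the knee were chosen after imaging, and chosen differently in the two groups, the comparison could be biased. That is conceivable because the only written permission for bilateral subjects sits in a list that also requires "Subjects will have a Zimmer Persona fixed bearing PS TKA", while the PCR site is not yet named. And with two scores on file, the documents do not say which one decides eligibility or which is set against the kinematics.

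**Working it through.** **Step 1. Which unit does the text support?**

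*Person or single knee:*
- Study design: 25 subjects assessed and 28 enrolled per implant type; one prosthesis per subject.
- Data Collection: the technician follows one implanted knee. For each participant, the curves describe one joint. Radiation time is capped once, at two minutes.
- Private Health Information/Medical Record Data: problems in the opposite knee are listed with back trouble and ankle fusion as conditions that may affect the results. The other knee is context, not a second observation.
- The same part of the Protocol, on data storage: one identifier per subject. No knee-level identifier is described.

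*Possibly knee:*
- The form instruction ("please use a different form for each knee") is pre-printed on a published questionnaire. It shows that two scores may exist, not that two knees are imaged.
- "All TKAs should be judged clinically successful (KSS > 75" reads naturally as a plural across subjects, given the sentence that follows it.
- "the necessary 25 usable datasets for analysis for each implant type" is the yield expected from 28 subjects, which allows for 3/28 = 10.7% loss. In context that is one dataset per subject.

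The form instruction is the only clear knee-level wording, and it concerns the questionnaire. The balance is one imaged knee per person.

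**Step 2. Error rate on that reading.** With one knee per person there are 25 independent values per group. Simulated under no true difference, choosing the knee at random gives 4.8 to 5.1%. Picking the larger of two knees in the same way in both groups, with equal bilateral numbers, gives 4.3 to 5.0%.

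**Step 3. Error rate if both knees were entered.** The documents give neither the number of bilateral people nor the correlation ρ. Assume five bilateral people, in one group or in each, and ρ = 0.3, 0.6 or 0.9. The variance ratio V is the true variance of the group difference divided by the variance the test assumes. The error rate is then roughly P(|Z| > 1.96/√V).

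- *25 people plus 5 second knees, in each group (30 knees per group):* V = 1 + 2·5·ρ/30.
- *The same in one group only:* V = [(1 + 2·5·ρ/30)/30 + 1/25] / [1/30 + 1/25].
- *25 knees from 20 people, in each group:* V = 1 + 2·5·ρ/25.

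| Case | ρ | V | Approximation | Simulated t-test (100,000 runs) |
|---|---|---|---|---|
| One group only | 0.3 / 0.6 / 0.9 | 1.045 / 1.091 / 1.136 | 5.5 / 6.1 / 6.6% | 5.5 / 6.0 / 6.7% |
| Both groups | 0.3 / 0.6 / 0.9 | 1.10 / 1.20 / 1.30 | 6.2 / 7.4 / 8.6% | 6.1 / 7.4 / 8.8% |
| 25 knees from 20 people, both groups | 0.3 / 0.6 / 0.9 | 1.12 / 1.24 / 1.36 | 6.4 / 7.8 / 9.3% | 6.4 / 7.9 / 9.3% |

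A separate run of the last case gave 6.5% at ρ = 0.3 and 9.4% at ρ = 0.9. With one bilateral person in each group and all knees entered, the figure is 5.4 to 5.9%. Fisher's test, at an assumed 30% lift-off rate and with five bilateral people in one or both groups, stays at or below 5.0%. At 50% lift-off with five in both groups it reaches 5.3% at most.

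**Step 4. Would anyone gain by using both knees?** The extra information from m second knees is m·[2/(1+ρ) − 1] people. For m = 5 this is 5·(2/1.3 − 1) = 2.7 at ρ = 0.3, 5·(2/1.6 − 1) = 1.25 at ρ = 0.6, and 5·(2/1.9 − 1) = 0.3 at ρ = 0.9. The pull towards double counting is weak.

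**The case for a change.** The strongest case for acting is that favouring a reading is not the same as prespecifying it. Several trials per activity are allowed in order to obtain usable images, and the target is counted in usable datasets. If the count falls short, nothing written stops a second knee from filling the gap or the knee from being chosen after imaging. If the larger knee were picked in the PS group only, with five bilateral subjects there, the group mean would shift by about 0.04 to 0.10 SD and the error rate would be about 5.2 to 5.9%. The rate grows with more bilateral people: with eight in each group and all knees entered, the t-test reaches 6.7 to 10.4%. A sentence in each document would close the question at no imaging cost.

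The silence is real, and a sentence would do no harm. But each of these outcomes needs staff to depart from the single-knee procedure that the Protocol describes, and then needs several bilateral subjects as well.

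The point about two scores is weaker. The form records the side of the knee being scored, so a score can be matched to the imaged knee for the planned correlation. On eligibility, "All TKAs should be judged clinically successful (KSS > 75" and "Subjects will have KSS greater than 75" can diverge only for a bilateral person whose knees fall on opposite sides of 75. That is a narrow wording matter and does not touch the validity of the tests.

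**Conclusion.** The gap exists, but it is missing detail and not an error in the analysis. The text favours one imaged knee per person, and on that reading the SAP's tests hold their 5% level. Inflation appears only if both knees are entered as independent values. With five bilateral subjects and ρ between 0.3 and 0.9, it is about 5.5 to 6.7% (one group), 6.1 to 8.8% (both groups) or 6.4 to 9.4% (25 knees from 20 people per group). Those figures rest on an assumed bilateral count and an assumed correlation, neither of which the documents give. An analyst following the Protocol would take one knee per person and match the score by side. No change to the plan is needed.
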